This is a randomized control, open-label, single-site clinical trial. We will target completion by eighty adolescents (age 12-17 years) with Type 1 diabetes and their parent/guardian (age 18+) to participate in a 3 month outpatient study. Participants will be randomized to either a Control Group or Experimental Group. Both groups will use the study continuous glucose monitor, study activity tracker, and a study insulin pen if an multiple daily injection (MDI) user. Subjects who use an insulin pump to treat their type 1 diabetes will use their personal insulin pump. All subjects will be asked to download this equipment and provide it to the study team each week. The study team will communicate weekly with each group. Questionnaires will also be completed at the beginning and at the end of the study. The Experimental Group will receive the CloudConnect Reports. The Control Group will not receive this feedback.

3. Does the study involve a placebo?

No

Human Participants

Ages: 12-17 years old and at least one of parent(s)/guardian(s) (age 18+)/guardian (adolescent/parent dyad is required for participation in this trial)

Sex: Male and Female

Race: All

1. Provide target # of subjects (at all sites) needed to complete protocol.

For the Pilot Study, up to 6 adolescents and 6 parent(s)/guardian(s) may complete the study. These pilot subjects may also participate in the Main Study.

For the Main Study, 160 subjects (80 dyads – consisting of 80 adolescents and 80 adults) need to complete the study.

2. Describe expected rate of screen failure/ dropouts/withdrawals from all sites.

We expect that because the length of the study it could be 20-30% dropouts/withdrawals from the study.

3. How many subjects will be enrolled at all sites?

This is a single site clinical trial to be completed at UVa.

4. How many subjects will sign a consent form under this UVa protocol?

Up to 210 subjects (105 dyads – consisting of 105 adolescents and 105 parent(s)/guardian(s)) will sign consent for the Main Study and up to 16 subjects (8 parent/child dyads) will sign a consent for the Pilot Study. i.e. total = 226 (210+16)

Inclusion/Exclusion Criteria

1. List the criteria for inclusion for Pilot and Main Study Adolescent Subjects

- Willingness to provide informed consent
- Adolescents ages ≥ 12 and ≤ 17 years old with a parent/guardian (18+ yo) who is willing to participate with the child

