Use of anti-diabetic agents other than short-acting insulin for CSII subjects or long-acting insulin for MDI subjects, including: metformin, sulfonylureas, meglitinides, thiazolidinediones, dipeptidyl peptidase 4 (DPP-4) inhibitors, glucagon-like peptide 1 agonists and alpha-glucosidase inhibitors

Statistical Considerations

1. Is stratification/randomization involved? Yes

► IF YES, describe the stratification/ randomization scheme.

During the main study, up to 210 adolescents, ages 12 years - 17 years (inclusive), will be recruited with one of their parent(s)/guardian(s), 18+ y.o., in each arm. Based on experience, approximately 40 adolescents & 40 parent(s)/guardian(s) in each arm will complete the study (N=80 adolescents and 80 parents, total 160 subjects). Male and female adolescents will be recruited, and all racial/ethnic groups will be eligible for participation. Participants will be recruited in randomization blocks of 4. The goal is to target a minimum of 10 participants in each of the 4 stratification subgroups based on age (12-14 y.o and 15-17 y.o.) and insulin therapy (CSII and insulin pen). ,

► IF YES, who will generate the randomization scheme?

Sponsor
 UVa Statistician. Answer/Response:
 UVa Investigational Drug Service (IDS)
 Other: Center for Diabetes Technology (CDT) personnel

2. What are the statistical considerations for the protocol?

The objectives section and the statistical section should correspond, and any objective for which analysis is unfeasible should be deleted. Also, the estimates and non-statistical assumptions of the statistical section should be supported by discussion in the background section.

The answer to this question should include:

-Study Design/Endpoints

- Recap of study objectives and endpoint definitions. An assessment of how study objectives will be assessed by identifying & defining which endpoints will be used to assess each component of the study objectives.
- The study design should include contingencies for early stopping, interim analyses, stratification factors (If applicable), and any characteristics to be incorporated in analyses.
- The power/precision of the study to address the major study endpoint(s), the assumptions involved in the determination of power/precision.

Study Design:

This study employs a randomized design in which one group of participants will be assigned to use the CloudConnect system and the other group to CGM using their insulin paramenters and treatments.

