Study Objectives & Endpoint Definitions:

As mentioned previously, this project seeks to assess how CloudConnect affects participant engagement, dyad engagement, and clinical outcomes in adolescent T1D.

We will assess how adolescents and their parent(s)/guardian(s) respond to this new approach using the Family Communication Inventory (FCI). This diabetes-specific approach was designed by the investigators to assess parent-child communication regarding tasks (discussion of insulin dosing for a given meal, BG trends, need for dose changes). As an outcome measure, scores for parents and adolescents are summed, with higher scores representing higher degree of engagement and T1D-specific communication.

Power/Precision of the study to address major study endpoints:

In using the FCI, we determined based on preliminary data from 220 adolescent/parent participants eligible for the study, with mean (90.3) and standard deviation (12.5) that we are powered to detect a difference of 8.5% in this outcome in the treatment group with 80% power and an alpha of 0.05. This study will require 40 adolescent participants with 40 parent(s)/guardian(s) to complete per arm. Assuming a non-adherence/drop-out rate of 20-30% for Intention-to-Treat (ITT) analysis, 55 participants is yielded per arm.

3. Provide a justification for the sample size used in this protocol.

The study team will attempt to enroll an equal number subjects based on gender, CSII, and MDI use. The study is powered to detect a difference of 8.5% in this outcome in the treatment group with 80% power and an alpha of 0.05. This study will require 40 adolescent participants with 40 parent(s)/guardian(s) to complete per arm. Assuming a non-adherence/drop-out rate of 20-30% for Intention-to-Treat (ITT) analysis, 55 participants is yielded per arm.

4. What is your plan for primary variable analysis?

Because this is a randomized study, our primary outcome (score on the Family Communication Inventory) will be by t-test comparing those randomized to CloudConnect to usual care+CGM. Comparison of secondary outcomes between treatment groups will also be t-tests. Secondary analyses of both the primary and secondary outcomes will utilize multivariable ANOVA, particularly in the event that key variables differ between groups. For example, if average steps per day [as a measure of exercise] is higher in one group vs.

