Subjects will be asked to provide weekly downloads of all equipment, including the subject's personal insulin pump. Subjects may be asked to repeat a data collection week if the data provided is insufficient or poor quality. The Experimental Group will receive the additional CloudConnect component consisting of a weekly

report based on analysis of the data gathered for each participant. After review by a study physician, the report will be sent via email once a week to both the adolescent participant and their parent(s)/guardian(s).

The weekly contact by phone, email or text will be to:

- Check for AE or SAE
- Remind to download all the data (i.e. CGM, insulin pump/insulin pen, Fitbit data)
- Ask standardized questions:
 - I. *During the past week, did you talk with your parents about your diabetes management?*
Yes or No
 - II. *If you answered “yes,” how good or bad was the tone of that conversation?*
(Likert scale: Very good good Neutral bad Very bad)
 - III. During the past week, did you change your insulin parameters?
(Yes=1, No=2)

Visit 4: End of Pilot Study – Return study equipment to study team via CRU (up to 15 minutes) or by FedEx pre-labeled shipment (up to 15 minutes)

A Hemoglobin A1c sample will not be collected at the end of the Pilot Study.

MAIN STUDY: The goal is to complete 160 subjects (80 dyads – consisting of 80 adolescents and 80 adults). A dropout rate of 20-30% is anticipated. Therefore, up to 210 subjects may sign consent with the goal of completing 160 study subjects. Both continuous subcutaneous insulin infusion (CSII) and Multiple Daily Injection (MDI) subjects are eligible to participate in this study.

Parent/Guardian Role:

The study team will ask one parent to serve as the ‘family spokesperson’. This parent will complete:

- the weekly questionnaires for consistency
- attend training sessions with subject
- download data to study team each week
- participate in the weekly communication with their child (both parents will be encouraged to participate in the weekly communication)

This parent and the adolescent will also be available for contact by the study team (e.g. by phone/text/email) regarding study compliance issues such as completing questionnaires and uploading of data from CGM, insulin pump, insulin pen (if MDI subject), and activity monitor.

Participation in the study will be about 4 months.

[figure not shown]
Randomization:

Subjects will be randomized to either a Control Group or an Experimental Group:

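### Main Study enrolment is capped at 105 consented dyads, but the power section calls for 110, and the stated 20-30% dropout supports the cap only up to about 24% loss

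*Combined protocol and SAP*

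**What the plan says.** The enrolment figures appear in four places in the combined protocol and SAP.

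- **Human Participants, items 1, 2 and 4.** The completion target is 160 people, or 80 dyads ("consisting of 80 adolescents and 80 adults) need to complete the study"). On losses: "We expect that because the length of the study it could be 20-30% dropouts/withdrawals from the study". The Main Study consent limit is "Up to 210 subjects (105 dyads", and a further 16 people may consent to the pilot, 226 in all.
- **Statistical Considerations, item 1 (randomization).** This section says that "up to 210 adolescents, ages 12 years - 17 years (inclusive), will be recruited with one of their parent(s)/guardian(s), 18+ y.o., in each arm". The next sentence gives about 40 adolescents and 40 parents per arm completing, 160 people in total.
- **Statistical Considerations, item 2 (Power/Precision), repeated in item 3.** "This study will require 40 adolescent participants with 40 parent(s)/guardian(s) to complete per arm". Then: "Assuming a non-adherence/drop-out rate of 20-30% for Intention-to-Treat (ITT) analysis, 55 participants is yielded per arm".
- **Study Procedures, Main Study.** "A dropout rate of 20-30% is anticipated. Therefore, up to 210 subjects may sign consent with the goal of completing 160 study subjects".

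Subject Compliance with Study Procedures adds that subjects withdrawn for non-compliance are replaced. It does not say how replacements count against the consent limit.

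**The concern.** All these sections start from the same two inputs, 80 completing dyads and 20-30% dropout, yet they end at different enrolment totals: 105 dyads in two places and 110 in the power section. The larger total exceeds the stated consent limit. The Main Study text also presents 210 subjects as following from the dropout range, although a range cannot yield a single number until one rate within it is chosen, and none is named.

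Forty completers per arm is the basis of the trial's only power statement. A reader cannot tell which total governs recruitment, or what dropout the trial can absorb before it misses that target.

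**Working it through.** **Inputs.** 80 completing dyads, 40 per arm (Human Participants item 1; Power/Precision). Dropout 20-30% (Human Participants item 2; Power/Precision; Main Study). Consent limit 210 people (Human Participants item 4; Main Study). Inflated size 55 per arm (Power/Precision). The 55 must count dyads, because the sentence before it requires 40 adolescents with 40 parents per arm.

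**1. The two totals.** 210 / 2 = 105 dyads. 55 × 2 = 110 dyads = 220 people. The gap is 5 dyads, or 10 people. Whether 55 counts consented or randomised dyads, at least 110 would have to consent, which is more than 105.

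**2. Reproducing the plan's figures.** Enrolment needed = completers / (1 − dropout), rounded up.

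| Dropout | Per arm, from 40 | Total, from 80 |
|---|---|---|
| 20% | 50 | 100 |
| 25% | 54 (53.3) | 107 (106.7) |
| 30% | 58 (57.1) | 115 (114.3) |

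Both stated figures come within 2 only at 25%, a midpoint the plan does not state. Worked backwards they imply different rates: 1 − 80/105 = 23.8% and 1 − 80/110 = 27.3%.

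**3. Expected completers.** Enrolled × (1 − dropout), taking every consented dyad as randomised. This is an upper bound for 105, since any screen failure after consent lowers it.

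| Dropout | 105 dyads | 110 dyads |
|---|---|---|
| 20% | 84 | 88 |
| 25% | 78.75 | 82.5 |
| 30% | 73.5 | 77 |

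If losses are independent, the binomial chance of at least 80 completers in total at 20, 25 and 30% loss is 86%, 44% and 10% with 105 dyads, and 98%, 75% and 31% with 110. Requiring 40 in each arm is stricter: 65%, 24% and 4% with arms of 53 and 52, and 87%, 51% and 15% with 55 and 55.

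**4. Effect on power.** Assumptions: two-sided t-test at 0.05, SD 12.5, and mean 90.3 and SD 12.5 describing the summed dyad score. The 8.5% is read as relative to the mean, 0.085 × 90.3 = 7.68 points, and every lost dyad is taken to lack an end-of-study FCI.

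| Completers | Power |
|---|---|
| 40/40 (planned) | 77.4% |
| 42/42 (105 dyads, 20% loss) | 79.4% |
| 37/36 (105 dyads, 30% loss) | 73.5% |
| 44/44 (110 dyads, 20% loss) | 81.3% |
| 39/38 (110 dyads, 30% loss) | 75.8% |

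The largest fall from 40/40 is 77.4 − 73.5 = 3.9 percentage points. If no FCI is lost, power is 87.6% (105) or 89.1% (110). If 8.5 means points, power is 85.2% at 40/40 and 81.7% at 37/36.

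**The case against.** The strongest reply is that the plan never undertakes to cover 30% loss. It gives a range as a possibility, sets a ceiling, and calls 160 completers a goal. Inflating at 25% gives about 107 dyads, and 105 and 110 lie on either side of it, so both look like rounding around a midpoint. This stands. It rules out reading the plan as wrong merely because 30% is not covered. It does not remove the disagreement between 105 and 110, and it confirms that the planning rate was left out.

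A second reply is that withdrawn subjects are replaced. Each replacement dyad must also consent, so replacements presumably use up the same 105. That is an inference, because the plan does not say so, but nothing in the text provides places above the limit.

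A third is that some lost dyads may still be analysed. The power section's rate covers non-adherence as well as dropout under intention-to-treat, dismissal is triggered by missed downloads, and questionnaires may be answered from home. This also stands, and it makes the power figures after loss a worst case.

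Two stronger readings are tempting. A reader might infer that the trial is seriously underpowered or must enrol 115 or more dyads; the documents set no such standard, and the power loss is small. A reader might also take the randomization section literally as 210 adolescents per arm; its next sentence, with 40 per arm completing and 160 people in total, shows this to be a slip for 210 subjects overall.

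**Conclusion.** The conflict is certain: the power section's 110 dyads cannot be enrolled under a consent limit of 105, and no other section reconciles them. The claim that 210 subjects follow from 20-30% dropout holds for only part of that range. Both totals suffice on average at 20%. At 25%, 110 suffices and 105 falls about one dyad short. At 30% both fall short, by 6.5 and 3 dyads.

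The consequence is modest. A loss of about 4 percentage points of power requires, together, 30% loss, the 105 total, the relative reading of 8.5%, and no end-of-study FCI from any lost dyad. This is a minor consistency correction and does not call the design into question.

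**What to change.** 1. Use one dyad total in Human Participants, Statistical Considerations items 1 to 3, and the Main Study text. Keeping the 105-dyad consent limit and restating 55 per arm as at most 52-53 per arm (105 / 2 = 52.5) adds no enrolment. Choosing 110 would raise the limit from 210 to 220 subjects, and the overall total from 226 to 236 with the pilot's 16; that cost should be stated.
2. In the randomization section, replace the per-arm wording with a limit of 210 subjects (105 dyads) in total, if that total is kept.
3. Say whether the power section's inflated figure counts consented or randomised dyads.
4. In the Main Study text, drop the inference from 20-30% to 210. Name the planning dropout rate and give the expected completers at 20% and 30% loss: 84 to about 73 for 105 dyads, as an upper bound if all consented dyads are randomised. Add that 80 completers are expected only up to about 24% loss.
5. Leave the power section's 80% figure to its own check. Printing a different power for 40 per arm in the Main Study text would create a new mismatch.

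If 105 is kept, the cost is text only, plus openly stating that the completion target is not expected to be met at the upper end of the dropout range.

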Visit 2 (may be combined with Visit 1, may be done via phone or video): Adolescent subjects will be randomized and trained on the use of the study CGM and Fitbit. The CGM will be inserted into their abdomen per manufacturer instructions. Both Control and Experimental Group subjects will use their own personal pump. If the subject uses multiple daily injections (MDI), a commercially available Bluetooth connected insulin pen (inPen) will be given to both the Control and Experimental subjects in order to be able to collect the data accurately about meal time bolus treatments. Both pump users and MDI subjects will use their personal insulin. Each group will provide the study team weekly downloads from the study equipment and the personal insulin pump. Weekly CloudConnect reports will be provided to the Experimental Group participants *only*.

Depending on the subjects/family preference, the study team contact subjects via phone calls, text messages and/or emails at least once a week during the trial to:

- a) Remind them to download and transmit the data
- b) Check for AEs or SAEs
- c) Ask weekly standardized questions

All subjects will be reminded on how to download study data, if necessary. Both groups may complete a 1-week run-in period if they are CGM-naïve to ensure they are comfortable with the use of the study equipment, that all the study devices work properly, and to address issues related to transmission of the data to the study team. This run-in period may be repeated as necessary up to 3 times at the request of the study subject or study team. This data will not be included as part of the 12 week data collection. For subjects who have CGM experience, the investigator will determine if it is appropriate for he or she to skip the run-in period.

Visit 3 Check-in (Week 8 / on-site, email, or phone):

Subjects will download diabetes equipment weekly and submit the data to the study team for 12 weeks. Subjects may be asked to repeat a week of data collection if the quality of the data is insufficient for analysis.

A Check-In with the adolescent and parent/guardian will be completed to evaluate compliance and to answer any questions that the adolescent or parent may have about the study.

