Visit 4 – End of Study (about Week 12): Subjects will be asked to return to the Clinical Research Unit (CRU) to return study equipment (i.e. Bluetooth pen, CGM, Fitbit), if possible. A post-study HbA1c test will be obtained with a point-of-care equipment or local laboratory (same method as screening collection). This can be omitted if it is not possible to go to a laboratory or come to the clinic because of governmental restrictions such as Stay-at-Home orders. Questionnaires will be completed electronically at the end of this visit. Questionnaires may be completed at home prior to this visit or at the CRU.

2. If this protocol involves study treatment, explain how a subject will be transitioned from study treatment when they have completed their participation in the study.

The study intervention is to evaluate the communication between the adolescent study subjects and their parents. The treatment for T1D is subcutaneous insulin either by using insulin pumps or insulin pens. This

treatment will remain the same at the completion of this study. Subjects will return to using their personal diabetes equipment and follow their own insulin parameters.

Subject Compliance with Study Procedures

- 1. Explain how the study team will monitor the subject for compliance with the study procedures.** A mid-study visit during Week 8 is planned to assess compliance. In addition, there will be at least 1 phone call or text message per week to remind subjects to download and transmit the required data, if needed.

It will be at the discretion of the investigator to determine if the patient is not compliant, i.e. three or more weeks with no data received, and the subject will be withdrawn for the study and replaced.

- 2. Describe criteria for when a subject is considered to be non-compliant with study procedures.**

The subject will be dismissed for the study if the subject misses 3 or more weeks of data downloads.

Bibliography

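### Dyads are randomised before an optional, repeatable device run-in, so skip and repeat decisions and any run-in losses fall after allocation in an open-label trial

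*Combined protocol and SAP*

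**What the plan says.** The Visit 2 text of the Main Study (under Study Procedures) opens with allocation and training together: "Adolescent subjects will be randomized and trained on the use of the study CGM and Fitbit". The run-in comes later in the same section: "Both groups may complete a 1-week run-in period if they are CGM-naïve". Its purposes are comfort with the equipment, and checking "that all the study devices work properly, and to address issues related to transmission of the data to the study team". It can be extended: "This run-in period may be repeated as necessary up to 3 times at the request of the study subject or study team". For experienced users, "the investigator will determine if it is appropriate for he or she to skip the run-in period". On the data from this period the plan says: "This data will not be included as part of the 12 week data collection".

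Other sections that bear on the point:

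- Study Design, item 2, describes the trial as open-label.
- Subject Compliance says that when the investigator judges a subject non-compliant, for example after three or more weeks with no data, "the subject will be withdrawn for the study and replaced".
- Statistical Considerations, items 2 and 3, refer to intention to treat when inflating the sample size for 20–30% non-adherence or dropout.
- The rationale under Objectives/Hypothesis promises a comparison with diabetes control before the intervention.
- The Main Study text lets Visits 1 and 2 be combined, and lets questionnaires be answered at home within a week of the visit.

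**The concern.** A device run-in does its job best before allocation. Dyads that cannot manage the devices or the data transfer then drop out without ever belonging to an arm, and the length of the run-in cannot depend on the arm. Here the order is reversed, with three consequences.

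First, whether to skip or repeat the run-in is a judgement without stated criteria, made by people who know the allocation. The gap between randomisation and the first counted week, and so between baseline and the final questionnaire and HbA1c, can differ between arms. The plan also does not say whether CloudConnect reports are sent during the run-in, so exposure in that period is undefined.

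Second, a dyad that stops during the run-in has been randomised. The plan does not say how it is counted, and the compliance rule could lead to its replacement. Replacing randomised dyads departs from an intention-to-treat comparison.

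Third, mean glucose and time in range are secondary outcomes with no CGM period before randomisation to adjust for.

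**Working it through.** **Order of events.** The Visit 2 text states randomisation first. It then describes the run-in for both groups, which presupposes that groups exist. The study design figure is not available in the text, but no passage places allocation after the run-in.

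**Delay.** A skipped run-in gives 0 weeks. One week plus three repeats gives 1 + 3 = 4 weeks (3 weeks if the limit of three counts the first week). The final assessment then falls 12 to 12 + 4 = 16 weeks after randomisation, which fits the stated total participation of about 4 months. The plan has therefore left room for the delay. It does not make the delay equal between arms.

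**Withdrawal rule.** Three or more weeks without data can lead to withdrawal and replacement. A run-in of three or four weeks with failed transmission could reach that count. The plan does not say whether run-in weeks count.

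**The plan's own sample size.** Inputs from Statistical Considerations, item 2: Family Communication Inventory (FCI) mean 90.3, SD 12.5, difference 8.5%, power 80%, alpha 0.05. I assume a two-sided test and read 8.5% as a share of the mean.

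- Difference: 0.085 × 90.3 = 7.68 points.
- n per arm = 2 × (1.960 + 0.842)² × 12.5² / 7.68² = 41.6, so 42. The plan says 40, where power by the normal approximation is 0.784. The plan's figure is reproduced closely.
- Inflation, 40/(1 − d): 50 at d = 20%, 55 at 27%, 58 at 30%. The stated 55 per arm lies within the plan's range.

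**Possible run-in loss.** The documents give neither the CGM-naïve share nor a stopping rate. I assume 30–70% and 5–15%, applied to the 105 dyads who may sign consent (the number randomised could be lower).

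- Low: 105 × 0.30 × 0.05 = 1.6 dyads, or 1.5%.
- High: 105 × 0.70 × 0.15 = 11.0 dyads, or 10.5%.

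**Effect on power with 55 per arm.** There are two cases.

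| Case | Completers per arm | Power |
|---|---|---|
| Run-in loss inside the 20–30% | 55 × 0.70 to 55 × 0.80 = 38.5 to 44.0 | 0.77 to 0.82 |
| Run-in loss of 1.5–10.5% on top | 55 × 0.70 × 0.895 to 55 × 0.80 × 0.985 = 34.5 to 43.3 | 0.72 to 0.82 |

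The first row is the plan as it stands. Nothing in the documents says that the second applies.

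**Baselines.** HbA1c and the questionnaires belong to Visit 1; no CGM period does. Because Visits 1 and 2 may be combined and questionnaires may follow within a week, the baseline FCI, which is the primary instrument, can also be completed after the dyad knows its arm.

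**The case against.** The run-in has no pass or fail rule. It exists to solve problems, and its remedy is repetition, not removal. It is optional and aimed mainly at CGM-naïve subjects. The dropout allowance is worded to include non-adherence and can already cover early device dropouts. The primary outcome is the FCI compared by t-test, which needs no CGM baseline, and a randomised comparison of the CGM outcomes is valid without one. No difference in run-in loss between arms has been shown. Repeats can also be requested by the subject, and run-in data are left out for both arms. Starting the run-in before allocation has a price too: it selects dyads who manage the devices, in a trial whose outcome is engagement.

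Most of this stands, and it rules out two stronger readings. A reader might infer that the plan throws away a pre-randomisation CGM baseline. It does not: the run-in follows randomisation, so no such baseline exists, and what is missed is the chance to collect one. A reader might also infer that power is reduced. That requires run-in loss on top of the allowance, which the documents do not state.

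The objection does not answer the arm-aware decisions, the possible difference in delay, or the missing analysis rule for randomised dyads who stop early beside a rule that permits replacement.

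**Conclusion.** The point holds as a design weakness that is cheap to remove. As written, decisions to skip or repeat the run-in come after open allocation, the delay before the 12 weeks can vary from 0 to about 4 weeks and can differ by arm, and dyads lost in that period are post-randomisation losses open to replacement. No CGM baseline before randomisation is collected, which matters only for the CGM secondary outcomes.

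The size is uncertain. About 2 to 11 of 105 dyads could be affected, but only under assumed rates. The effect on power is nil if these losses are already in the 20–30%. Bias between arms is a risk that the order of events creates, not something the documents demonstrate. The conclusion about order rests on the Visit 2 text, since the design figure could not be read.

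**What to change.** - Keep device training at Visit 2, with the same alarm and app instruction for everyone at that stage. The group descriptions call alarms and apps optional only for the Control Group, and the Main Study text counts them as part of the difference between groups, so any arm-specific handling must wait for allocation.
- Keep the allocation concealed. Release it through the existing phone, text or email contact when the run-in ends or when the decision to skip it is recorded.
- Require the baseline questionnaires to be completed before release.
- Start the 12 weeks, the first report and any arm-specific alarm or app handling from release.
- State that every dyad allocated from then on is analysed in its assigned arm, and reconcile the withdraw-and-replace text with this.
- Optionally, use CGM data from the last run-in week as a covariate in the secondary CGM analyses, with a missing-baseline indicator. It would exist mainly for CGM-naïve dyads and may already reflect the early effect of new CGM access that the rationale expects.

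The cost is a wording change and remote release of the allocation, with no extra visit and no change to the 40 completers per arm. Some dyads learn their arm a few weeks later, and leaving out dyads who stop in the run-in narrows generalisability slightly.
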